2.3 Secondary Objectives and Endpoints

Secondary Objective	Endpoint(s)	Time Frame

Pilot Study - Ketamine Page 15 of 55

1.	To characterize the preliminary safety and tolerability of K-MaP in patients with stage 3 and 4 GI cancers.	 Adverse events (AEs), Unexpected AEs, and Serious AEs, by CTCAE (v.5.0). Vital signs (heart rate and blood pressure) Patient-reported outcome: challenging experiences (CEQ) 	 Day -28 through Day 35. Day 0 (multiple time points on day of ketamine administratio n). Day 0, 3-4 hours after ketamine administratio n.
2.	To assess the magnitude and durability of improvement from randomization in psychosocial distress.	 Clinician-rated outcomes: Global clinical impression of severity(CGI-S), Demoralization (DI), Mood symptoms (GRID-HAMD-6). Patient-reported outcomes: Demoralization (DS-II), Depression (PHQ9), Anxiety (GAD7), Quality of Life (FACIT-PaI-14). 	From Day -28 to Day 35.
3.	To assess the magnitude and durability of improvement from randomization in pain.	Patient-reported outcome: pain (BPI-SF)	From Day -28 to Day 35.
4.	To assess the magnitude of change from randomization in opioid analgesic use.	Patient-reported outcome: Opioid use (<24hr morphine milligram equivalence [MME])	From Day -28 to Day 35.
5.	To assess the magnitude of change from randomization in interoceptive awareness.	Patient-reported outcome: interoceptive awareness (MAIA-2)	From Day 0 to Day 7

Pilot Study - Ketamine Page 16 of 55

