After two MaP sessions, participants will receive ketamine on Day 0. This session will last about 4 hours. Participants will arrive to the Neurosciences Clinical Research Unit (NCRU) of the Sandler Building at UCSF Mission Bay, where they will be oriented to the treatment room for this study, which will contain a couch or bed for the participant to lie on in a private setting. Participants will hand over their shoes, keys, wallet, and phone to the study clinicians for safekeeping; these will all be returned to the participant upon completion of the treatment session. They will then complete all prerandomization assessments described in Section 6 of this study protocol. The ketamine session will be audio and video recorded, but participants will have the option of requesting that the recording be paused momentarily if they wish to discuss matters that are too personal to be recorded. There will be an on-site study physician (MD or DO) with 1) experience in the management of psychiatric emergencies and 2) experience or certification in the management of cardiovascular emergencies. Ketamine, its administration, and the medication visit will be paid for by the study and will not be billed to participants or their insurance.

Pilot Study - Ketamine Page 24 of 55

During the medication session, vital signs (heart rate and blood pressure) will be recorded at 10 minutes prior to ingestion of the oral solution ("Minute -10"), and then 30, 60, 90, 120, and 180 minutes after oral ingestion. If at 180 minutes blood pressure is meaningfully elevated compared to Minute -10, blood pressure will continue to be repeatedly assessed until it has returned to near its Minute -10 measurement. Respiratory rate and oxygen saturation will be assessed as needed.

In the event of elevated blood pressure prior to study drug administration

If the Minute -10 assessment (the mean of at least two readings separated by at least 2 minutes) of blood pressure exceeds either 140 systolic or 90 diastolic, periodic blood pressure readings will be obtained (e.g. at 5-minute intervals) to determine if the elevation may be temporary (e.g. due to anticipatory anxiety). If blood pressure decreases to (or below) 140 systolic and 90 diastolic within 20 minutes, study drug administration will proceed.

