Patient-reported outcomes characterizing the Ketamine experience—the Mystical Experience Questionnaire (MEQ) and the Challenging Experience Questionnaire (CEQ)—will be obtained on Day 0 after the medication effects have worn off (about 1.5-2 hours after Ketamine administration).

Pilot Study - Ketamine Page 28 of 55

Clinician-rated outcomes of global clinical impression of severity (CGI-S), demoralization (DI), and mood symptoms (GRID-HAMD-6) will be assessed at baseline, immediately prior to randomization, and post-ketamine administration on days 14 and 35.

As a safety measure, the Columbia suicidality rating scale (CSSRS) will be given at every study visit (Visits 1-9, starting on Day -28 to Day 35). Trained study staff will assess the participant for onset or exacerbation of suicidal idealization or behavior. If at any time the participant is unwilling to continue the study, they will be allowed to stop (except while under the acute effects of study drug ketamine on Day 0/Visit 2). Support services from therapists and clinicians will be available to the participant at each study visit. The participant will continue receiving their regular medical care, separate from this study.

Patient-reported measures include:

- Demoralization Scale-II (DS-II): A well-validated self-report measure of demoralization [4]. This 16-item, 3-point scale has a 2-week recall period and produces a total score than can range 0-32, with higher scores indicating a greater degree of demoralization. It has also been validated for use with Spanish-speaking patients from both Spain and Latin America [5].
- Patient Health Questionnaire-9 (PHQ-9): A validated and widely-used 9-item, 4-point scale (0 = "Not at all" to 3 = "Nearly every day") that assesses depression symptom severity with a 2-week recall period [74]. Higher scores indicate worse depression. The scale has also been validated in Spanish [75].
- General Anxiety Disorder-7 (GAD-7): A validated self-report measure for the severity of generalized anxiety disorder (GAD) symptoms. This 7-item, 4-point scale (0 = "Not at all" to "3 = Nearly every day") scale has 2-week recall period. Item scores are summed to produce a total score that can range 0-21, with higher scores indicating greater severity of symptoms of GAD [76]. The measure has been validated in Spanish [77].

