- Cogulation tests: PT/INR (for patients with a history of cirrhosis or GI bleed within past 6 months)
- Renal function: Creatinine.

Pilot Study - Ketamine Page 33 of 55

³ The following laboratory tests are required at baseline:

⁴ EKG is required at baseline.

⁵ DS-II will be measured two times before enrollment. Once over the phone after verbal waiver of consent, and tagain, ≥7 days apart, after the participant has signed the informed consent form and started screening procedures. DS-II will also be measured at Visits 4 (before Ketamine administration), 6, 8, and 9.

	≥7, ≤28 days before Enrollment	Day -28 to -7	Day -13 to -4	Day -12 to -1	Day 0	Day 3 +/- 2 days	Day 7 +/- 2 days	Day 11 +/- 2 days	Day 14 +/-2 days	Day 35 +/- 2 days
	Phone Screening	V1 [Enrollment/ Baseline]	V2 [MaP Session 1]	V3 [MaP Session 2]	V4 [Randomization/ Ketamine]	V5 [MaP Session 3]	V6	V7 [MaP Session 4]	88	۸9
PHQ9, GAD7, BPI-SF, <24hr MME,		Х			х		х		x	х
MAIA-2					х		х			
FACIT-Pai14		Х			х		х		х	х
CGI-S, DI, GRID-HAMD6		х							х	х
MEQ, CEQ					х					
MaP Therapy Session ⁶			х	х		х		х		
Ketamine therapy (day of administration) ⁷					x					
HBD Task ⁸					х					

Pilot Study - Ketamine Page 34 of 55

⁶ It will be recommended that att least one MaP session prior to Day 0/Visit 4 occur in-person (i.e., MaP sessions on Visit 2 or 3).

⁷ The ketamine administration visit will last approximately 4-5 hours. Patients will leave the premises once they are deemed to be free of the acute effects of ketamine, at least 3 hours have passed since ingestion of the oral drug-cranberry juice solution, and the study team confirms they are in the presence of a caregiver. In the event that a participant did not arrange a caregiver to accompany them home, the participant will be required to stay with the study staff and will be escorted outside by a study team member who will accompany them home in a taxi, Lyft, or Uber.

⁸ The Heartbeat Detection (HBD) task will be administered by a trained provider twice on the day of ketamine dosing. The tasks takes about 8 minutes to complete and will administered once a least 15 minutes prior to receipt of the oral drug-cranberry juice solution and again at least 3 hours after receipt of this oral solution.

	≥7, ≤28 days before Enrollment	Day -28 to -7	Day -13 to -4	Day -12 to -1	Day 0	Day 3 +/- 2 days	Day 7 +/- 2 days	Day 11 +/- 2 days	Day 14 +/-2 days	Day 35 +/- 2 days

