Secondary Objective #2: To assess the magnitude and durability of improvement from randomization in psychosocial distress associated with K-MaP, we will measure mean trends in patient-reported outcomes (DS-II, PHQ9, GAD7, FACIT-PAL-14 scores) in each study arm from baseline visit (Day -28 to -7) to post-ketamine (on Days 7, 14, and 35). In addition, we will calculate the proportion of participants per arm who no longer meet criteria for moderate-to-severe demoralization (i.e., DS-II > 10) post-ketamine. We will also measure mean trends in clinician-rated outcomes (CGI-S, DI, and GRID-HAMD-6 scores) per arm as above. ANCOVA models of follow-up endpoints as a function of study arm, adjusted for endpoints at baseline and randomization, will be conducted [110]. ANCOVA results will be presented graphically via mean trends per arm overlaid on individual trends, and via the mean (95% CI) difference between arms at Day 35. Cohen's d will be calculated at each follow-up time to estimate effect sizes. Any missing data will be estimated through the use of single imputation with baseline observations carried forward.

Secondary Objective #3: We will evaluate BPI-SF scores analogously to DS-II scores.

Secondary Objective #4: We will evaluate opioid analgesia use analogously to DS-II scores.

Secondary Objective #5: We will be using pair t-tests to measure mean changes in MAIA-2 scores in each study arm from prior to ketamine administration (on Day 0) to post-ketamine (on Day 7).

Secondary Objective #6: To assess how participants' subjective experiences with ketamine may be related to clinical outcomes, subjective reports of each participant's ketamine experience (videorecorded from Day 0) will be transcribed, inductively coded, and qualitatively analyzed to identify phenomenological content. In addition, participant MEQ and CEQ scores, which provide summary measures of the intensity of ketamine's acute effects, will be evaluated for potential correlation with trends in DS-II, BPI-SF, and opioid use.

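### The study calendar leaves out the pre-dose clinician ratings that Section 6 requires and the 9.2.3 ANCOVA uses; 9.2.3 also points to a Day 7 clinician rating that is not scheduled

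*Combined protocol and SAP*

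**What the plan says.** Secondary Objective 2 (Section 2.3) is "To assess the magnitude and durability of improvement from randomization in psychosocial distress". It has seven outcomes: three rated by clinicians (CGI-S, DI, GRID-HAMD-6) and four reported by patients (DS-II, PHQ9, GAD7, FACIT-Pal-14).

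Three places deal with when the clinician-rated scales are obtained or used:

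- **Section 6, Study Procedures and Schedule of Events:** the scales "will be assessed at baseline, immediately prior to randomization, and post-ketamine administration on days 14 and 35".
- **Section 6.1, Study Calendar:** the row "CGI-S, DI, GRID-HAMD6" is marked at V1, V8 (Day 14) and V9 (Day 35), and nowhere else.
- **Section 9.2.3, Secondary Objective #2:** the plan is to measure "mean trends in clinician-rated outcomes (CGI-S, DI, and GRID-HAMD-6 scores) per arm as above". The sentence this refers back to runs "from baseline visit (Day -28 to -7) to post-ketamine (on Days 7, 14, and 35". The model is then given: "ANCOVA models of follow-up endpoints as a function of study arm, adjusted for endpoints at baseline and randomization, will be conducted". Missing values are filled by "single imputation with baseline observations carried forward".

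For Day 0, Section 5 tells staff about participants: "They will then complete all prerandomization assessments described in Section 6 of this study protocol".

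**The concern.** The text of Section 6 and the calendar inside it disagree on whether clinicians rate the participant before dosing on Day 0. The analysis section assumes that they do. A rating of the pre-dose state cannot be made after dosing, so a missed one is gone.

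The reference point matters because MaP sessions 1 and 2 fall between Visit 1 and Day 0. Without the Day 0 rating, within-arm change on the clinician scales can only start at Visit 1. It then mixes the effect of two therapy sessions with whatever follows ketamine, whereas the objective asks for improvement from randomization.

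The Day 7 follow-up is a second mismatch, between 9.2.3 on one side and both schedules on the other.

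**Working it through.** **1. The schedules side by side**

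| Source | V1 | V4, pre-dose | V6 (Day 7) | V8 (Day 14) | V9 (Day 35) |
|---|---|---|---|---|---|
| Section 6 text, clinician scales | yes | yes | no | yes | yes |
| 6.1 row, clinician scales | yes | **no** | no | yes | yes |
| 9.2.3 read literally, clinician scales | yes | yes (covariate) | **yes** | yes | yes |
| 6.1 rows for DS-II, PHQ9/GAD7 and FACIT-Pal-14 | yes | yes | yes | yes | yes |

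The calendar has ten visit columns (phone screen and V1 to V9). The clinician row fills all ten cells, so the blank at V4 is not a column shift from PDF extraction. The patient-reported rows of the same calendar do carry a V4 mark.

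**2. Number of ratings**

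Assume 12 participants at every time point. Ratings per time point = 12 x 3 scales = 36.

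- 9.2.3 read literally: 5 x 36 = 180
- Section 6: 4 x 36 = 144
- Calendar: 3 x 36 = 108

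Following the calendar instead of Section 6 loses 144 - 108 = 36 pre-dose ratings. Reading 9.2.3 literally implies a further 180 - 144 = 36 ratings on Day 7 that neither schedule provides.

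**3. Can the imputation rule supply the covariate?**

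The 9.2.3 model for a follow-up score Y is

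Y = a + b x arm + c x (Visit 1 value) + d x (Day 0 value) + error.

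If Day 0 was never rated, carrying the baseline forward sets the Day 0 value equal to the Visit 1 value, and the model becomes

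Y = a + b x arm + (c + d) x (Visit 1 value) + error.

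Only the sum c + d can be estimated. In a check with 6 participants per arm, the design matrix had rank 4 of 4 with a real Day 0 value and rank 3 of 4 with the copied one. The arm effect b can still be estimated and is exactly the Visit 1-adjusted effect. The adjustment for status at randomization is what disappears.

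Residual degrees of freedom with 12 participants:

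- both covariates observed: 12 - 4 = 8
- Visit 1 only, or Day 0 copied from it: 12 - 3 = 9

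The effect on precision depends on the correlations between Visit 1, Day 0 and follow-up scores. The documents do not give them, so no precision figure is claimed.

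**4. A related small point: CEQ**

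Under Secondary Objective #1, 9.2.3 sends the CEQ to the same ANCOVA. The CEQ is collected once, after dosing, and asks about the medication session. It can have neither a baseline nor a randomization value. No CEQ data are lost, but the stated model cannot be fitted. A comparison of arm means has 12 - 2 = 10 degrees of freedom.

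**The case against.** The best reply is that the documents nearly settle the matter themselves. Section 5 sends Day 0 staff to Section 6. Section 6 describes its text as the detail and the calendar as the outline, and a blank cell in an outline does not cancel an explicit sentence in the detail. The objective and the ANCOVA both presuppose a randomization value, so the calendar is the lone outlier and looks like a clerical slip. This makes a missed rating less likely. It does not remove the contradiction: 6.1 is part of Section 6, so the pointer in Section 5 fits both schedules. Section 9.8 also ties case report form entry to the CTMS study calendar. The documents do not say how that calendar is built; if it copies 6.1, no Visit 4 clinician form would be prompted.

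On Day 7, one can read the cross-reference in 9.2.3 as meaning only the same method. That reading is possible, since 9.2.3 never names a Day 7 clinician rating outright. But the sentence referred to lists Day 7, and 9.2.3 goes on to plan Cohen's d at every follow-up time. The wording needs to be made definite. No scheduled data are lost, and the one between-arm difference that 9.2.3 says it will present is at Day 35, which both schedules cover.

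The consequence is limited, and that part of the objection stands. The Visit 1-adjusted arm difference and the trends from the baseline visit remain estimable. The outcomes are secondary, 9.1.1 plans no formal efficacy tests, and its go-forward rules use only DS-II and treatment-related SAEs. DS-II is marked at V4. The totals of 180, 144 and 108 are also approximate, because anyone who leaves between Visit 1 and Day 0 adds Visit 1 ratings. The 36 at Visit 4 follows directly from the 12 to be randomized.

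**Conclusion.** The inconsistency is real and should be fixed. Section 6 requires a pre-dose clinician rating on Day 0 and the calendar omits it. If the calendar is followed, up to 36 ratings are lost for good, a quarter of the 144 that Section 6 plans. The loss covers 3 of the 7 Objective 2 outcomes, all of the clinician-rated ones. Their change from randomization could then not be estimated, and the second ANCOVA covariate would not exist; the imputation rule only copies Visit 1. The Day 7 mismatch in 9.2.3 and the CEQ model are smaller wording faults.

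The loss is conditional on staff or the data system following 6.1, and the counts assume 12 participants at each time point. The primary feasibility endpoints and DS-II are not affected.

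**What to change.** - In 6.1, mark V4 (pre-dose) in the row for CGI-S, DI and GRID-HAMD-6.
- In 9.2.3, Secondary Objective #2, state that the follow-up days for these three scales are 14 and 35. Section 6, 6.1 and 9.2.3 would then describe the same 144 ratings.
- In 9.2.3, Secondary Objective #1, replace the ANCOVA for CEQ by an unadjusted difference in arm means with its 95% CI (10 degrees of freedom).

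The cost is one calendar row and two sentences. The only added work is a short clinician rating on Day 0, which Section 6 already requires. This does not settle a separate mismatch: 9.2.3 starts its trends at the baseline visit for all seven outcomes, while the objective is worded from randomization.

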6.1 Study Calendar

	≥7, ≤28 days before Enrollment	Day -28 to -7	Day -13 to -4	Day -12 to -1	Day 0	Day 3 +/- 2 days	Day 7 +/- 2 days	Day 11 +/- 2 days	Day 14 +/-2 days	Day 35 +/- 2 days
	Phone Screening	V1 [Enrollment/ Baseline]	V2 [MaP Session 1]	V3 [MaP Session 2]	V4 [Randomization/ Ketamine]	V5 [MaP Session 3]	V6	V7 [MaP Session 4]	8/	6/
Verbal Waiver of Consent; Phone Screen	х									
Informed Consent Form		х								
Brief Clinical Interview ¹		х			х					
Interview on Acceptability and Tolerability										х
Demographics		х								
C-SSRS		х	х	х	х	Х	х	х	х	х
Physical exam		х								
Vitals (BP, HR) ²		х			х					

Pilot Study - Ketamine Page 32 of 55

¹ Partcipants will be briefly interviewed by the study team at baseline. The baseline interview will asses for clinical fit for K-MaP by evaluating participant expectations and prior experiences of altered states of consciousness. On Day 0/Visit 4, around 1.5-2 hours after ketamine administration (when the drug effects wear off), the facilitators will engage the participant in a therapeutic interview to explore the experience they had. The Day 0/Visit 4 interview will be video and audio recorded.

² Vitals will be taken at baseline, and prior to ketamine administration on Day 0/Visit 4. On Day 0, vital signs (heart rate and blood pressure) will be recorded at 10 minutes prior to drug ingestion ("Minute -10"), and then 30, 60, 90, 120, and 180 minutes after drug ingestion. If at 180 minutes blood pressure is meaningfully elevated compared to Minute -10, blood pressure will continue to be repeatedly assessed until it has returned to near its Minute -10 measurement. Respiratory rate and oxygen saturation will be assessed as needed.

	≥7, ≤28 days before Enrollment	Day -28 to -7	Day -13 to -4	Day -12 to -1	Day 0	Day 3 +/- 2 days	Day 7 +/- 2 days	Day 11 +/- 2 days	Day 14 +/-2 days	Day 35 +/- 2 days
	Phone Screening	V1 [Enrollment/ Baseline]	V2 [MaP Session 1]	V3 [MaP Session 2]	V4 [Randomization/ Ketamine]	V5 [MaP Session 3]	9/	V7 [MaP Session 4]	V8	6/
Height and Weight		х								
Medical/Psychiatric Hx		х								
PPSv2		Х								
Eligibility Verification		X								
Randomization					х					
LFTs, Creatinine, Electrolytes, PT/INR ³		х								
12-lead EKG ⁴		х								
DS-II ⁵	Х	Х			х		Х		Х	х

- Electrolytes: Sodium, potassium, carbon dioxide, and chloride.
- Liver function tests: Total bilirubin, ALT, AST, and alkaline phosphatase.
- Cogulation tests: PT/INR (for patients with a history of cirrhosis or GI bleed within past 6 months)
- Renal function: Creatinine.

Pilot Study - Ketamine Page 33 of 55

³ The following laboratory tests are required at baseline:

⁴ EKG is required at baseline.

⁵ DS-II will be measured two times before enrollment. Once over the phone after verbal waiver of consent, and tagain, ≥7 days apart, after the participant has signed the informed consent form and started screening procedures. DS-II will also be measured at Visits 4 (before Ketamine administration), 6, 8, and 9.

	≥7, ≤28 days before Enrollment	Day -28 to -7	Day -13 to -4	Day -12 to -1	Day 0	Day 3 +/- 2 days	Day 7 +/- 2 days	Day 11 +/- 2 days	Day 14 +/-2 days	Day 35 +/- 2 days
	Phone Screening	V1 [Enrollment/ Baseline]	V2 [MaP Session 1]	V3 [MaP Session 2]	V4 [Randomization/ Ketamine]	V5 [MaP Session 3]	V6	V7 [MaP Session 4]	88	۸9
PHQ9, GAD7, BPI-SF, <24hr MME,		Х			х		х		x	х
MAIA-2					х		х			
FACIT-Pai14		Х			х		х		х	х
CGI-S, DI, GRID-HAMD6		х							х	х
MEQ, CEQ					х					
MaP Therapy Session ⁶			х	х		х		х		
Ketamine therapy (day of administration) ⁷					x					
HBD Task ⁸					х					

Pilot Study - Ketamine Page 34 of 55

⁶ It will be recommended that att least one MaP session prior to Day 0/Visit 4 occur in-person (i.e., MaP sessions on Visit 2 or 3).

⁷ The ketamine administration visit will last approximately 4-5 hours. Patients will leave the premises once they are deemed to be free of the acute effects of ketamine, at least 3 hours have passed since ingestion of the oral drug-cranberry juice solution, and the study team confirms they are in the presence of a caregiver. In the event that a participant did not arrange a caregiver to accompany them home, the participant will be required to stay with the study staff and will be escorted outside by a study team member who will accompany them home in a taxi, Lyft, or Uber.

⁸ The Heartbeat Detection (HBD) task will be administered by a trained provider twice on the day of ketamine dosing. The tasks takes about 8 minutes to complete and will administered once a least 15 minutes prior to receipt of the oral drug-cranberry juice solution and again at least 3 hours after receipt of this oral solution.

	≥7, ≤28 days before Enrollment	Day -28 to -7	Day -13 to -4	Day -12 to -1	Day 0	Day 3 +/- 2 days	Day 7 +/- 2 days	Day 11 +/- 2 days	Day 14 +/-2 days	Day 35 +/- 2 days
	Phone Screening	V1 [Enrollment/ Baseline]	V2 [MaP Session 1]	V3 [MaP Session 2]	V4 [Randomization/ Ketamine]	V5 [MaP Session 3]	9/	V7 [MaP Session 4]	٧8	6/
Concomitant Meds.		х	х	х	х	х	х	х	х	х
Adverse Events			Х	х	х	Х	Х	Х	Х	Х

Pilot Study - Ketamine Page 35 of 55

7 Participant Registration

A verbal waiver of consent will be obtained to collect only information essential for the screening call that will be conducted by phone or teleconference.

At the Enrollment study visit (Visit 1), a written, signed, informed consent form (ICF) and a Health Insurance Portability and Accountability Act (HIPAA) authorization must be obtained before any study-specific assessments are initiated. A copy of the signed ICF will be given to the subject and a copy will be filed in the medical record. The original will be kept on file with the study records.

All participants consented to the study will be registered in OnCore[®], the UCSF Helen Diller Family Comprehensive Cancer Center Clinical Trial Management System (CTMS). The system is password protected and meets HIPAA requirements.

